2.5.4 Windows for time points

For the safety assessment, the reference date for the derivation of relative days of events or findings will be the date of first IMP administration. Selected safety variables will be summarized by the analysis window define in [Table 3](#) for the by visit descriptive analysis. All available values from central lab will be assigned to the appropriate visit window. In the event of multiple measurements of the same test in the same window, the one closest to the targeted visit date will be used for the by-visit summary. If they are at the same distance to the target day, the latest one will be used. For procedures planned on Visit 2, if it is done on the same date as the first IMP injection but the performance time is missing, it will belong to Visit 2 time window.

Table 3 – Time window for safety endpoints

Visit	Target Day	Time windows for					
		Vital signs	Clinical lab testing	Serum Pregnancy test ,Hepatitis screen, HIV screen, ANA and Anti-ds DNA antibody	Urine Pregnancy test	Hepatitis B viral load	ECG
Visit 1 (Week -4±1)	-28±7	<-14	<-14	1-			
Visit 2 (Week 0)	1	-14-1-	-14-1-		1-	1-	1-
Visit 3 (Week 2)	15						
Visit 4 (Week 4)	29	1+-112			1+-42		
Visit 5 (Week 6)	43						
Visit 6 (Week 8)	57				43-70		
(Week 12)	85				71-98		
Visit 7 (Week 16)	113		1+-140		99-126	1+-140	
(Week 20)	141				127-154		
Visit 8 (Week 24)	169	113-224	141-224		155-182	141-266	

Visit	Target Day	Time windows for					
		Vital signs	Clinical lab testing	Serum Pregnancy test ,Hepatitis screen, HIV screen, ANA and Anti-ds DNA antibody	Urine Pregnancy test	Hepatitis B viral load	ECG
(Week 28)	197				183-210		
(Week 32)	225				211-238		
(Week 36)	253				239-266		
Visit 9 (Week 40)	281	225-322	225-322		267-294		
(Week 44)	309				295-322		
(Week 48)	337				323-350		
Visit 10 (Week 52)	365	323-406	>322		351-406	>266	1+
Visit 11 (Week 64)	449	>406			>406		

1-: up to 1st dose date/time; 1+: after 1st dose date/time;

For the efficacy assessment, the reference date for the derivation of relative days of events or findings will be the randomization day. If a patient receives IMP prior to the randomization by mistake, the reference date of efficacy assessment will be the date of the first IMP administration for that patient. For the primary analyses, all available values of scheduled measurements will be assigned to the appropriate visit window according to [Table 4](#). In the event of multiple measurements of the same test in the same window, the one closest to the targeted visit date will be used for the by-visit summary. If they are at the same distance to the target day, the latest one will be used. For the on-treatment sensitivity analyses, only scheduled measurements collected during the treatment epoch will be assigned to a time window.

Table 4 – Time window for efficacy variables

Visit	Target Day	Time windows for						
		Nasal endoscopy	CT scan	UPSIT	VAS for rhinosinusitis, sense of taste	Spirometry, ACQ-6	EQ-5D	SNOT-22
Visit 1 (Week -4±1)	-28±7	<-14						
Visit 2 (Week 0)	1	-14-1	1	1	1	1	1	1
Visit 3 (Week 2)	15			1+-21	1+-21			
Visit 4 (Week 4)	29	1+-42		22-70	22-42	1+-70		1+-42
Visit 5 (Week 6)	43							
Visit 6 (Week 8)	57	43-84			43-84			43-84
Visit 7 (Week 16)	113	85-140		71-140	85-140	71-140	1+-140	85-140
Visit 8 (Week 24)	169	141-224	1+-266	141-266	141-224	141-224	141-224	141-224
Visit 9 (Week 40)	281	225-322			225-322	225-322	225-322	225-322
Visit 10 (Week 52)	365	323-406	>266	>266	323-406	>322	>322	>322
Visit 11 (Week 64)	449	>406			>406			

1-: up to randomization and before 1st dose date/time; 1+ : after randomization or 1st dose date/time

For the pharmacokinetics/pharmacodynamics variables summary, the reference date for the derivation of relative days of measurements will be the date of first IMP administration if the

patient is treated with study treatment, or the randomization date if the patient is not treated. Pharmacokinetics /pharmacodynamics variables will be summarized by the analysis window defined in Table 5 for the by visit descriptive analyses. All available values of measurements will be assigned to the appropriate visit window. In the event of multiple measurements of the same test in the same window, the one closest to the targeted visit date will be used for the by-visit summary. If they are at the same distance to the target day, the latest one will be used. For procedures planned on Visit 2, if it is done on the same date as the first IMP injection but the performance time is missing, it will belong to Visit 2 time window.

Table 5 – Time window for pharmacokinetics/pharmacodynamics variables

Visit	Target day	Time windows for		
		TARC, Eotaxin-3, periostin, total IgE, antigen-specific IgE	Serum dupilumab concentration	Anti-drug antibodies
Visit 1 (Week -4±1)	-28±7			
Visit 2 (Week 0)	1	1-	1-	1-
Visit 3 (Week 2)	15		1+-21	
Visit 4 (Week 4)	29		22-70	
Visit 5 (Week 6)	43			
Visit 6 (Week 8)	57			1+-84
Visit 7 (Week 16)	113		71-140	85-140
Visit 8 (Week 24)	169	1+-266	141-224	141-266
Visit 9 (Week 40)	281		225-322	
Visit 10 (Week 52)	365	>266	323-406	267-406
Visit 11 (Week 64)	449		>406	>406

1-: up to 1st dose date/time or randomization if patient is not treated; 1+: after 1st dose date/time or randomization date if patient is not treated;

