#### **10.1.15 Visit 11 (Week 64): End of study**

- PRO Patient administration in the e-diary:
  - Daily symptoms of NC, loss of smell and anterior and posterior rhinorrhea,
  - VAS for rhinosinusitis,
  - Reduced sense of taste symptom severity score.
- Inquire about AEs/SAEs and background therapy tolerability.
- Collect NIMP boxes
- Record all medication use with start date and dose in the e-CRF.
  - Check for use of prohibited medications.
  - Complete rescue medication/surgery page (s) of e-CRF. Use of oral steroids for rescue treatment of worsening nasal polyps or for another reason will be captured by the Investigator (or designee) on the appropriate page(s) of the e-CRF page and the date and dosing information (daily dose, duration, INN) will be informed. Details on planned date for surgery, type, and outcome (whenever possible) of surgery will be recorded in a specific e-CRF page. If surgery is performed during the study treatment period or follow-up an AE or SAE page will be completed.
- Call IVRS/IWRS to register visit.
- Download e-diary/NPIF meter and review the data; collect eDiary device.
- Measure vital signs (blood pressure, heart rate, respiration rate, body temperature, weight).
- Perform physical examination.
- Perform nasal endoscopy and send to Central Reader.
- Obtain urine  $\beta$ -HCG pregnancy test if WOCBP.
- Obtain blood samples:
  - Hematology (see [Section 9.4.2](#) for details),
  - Serum chemistry (see [Section 9.4.2](#) for details).
- Perform blood sampling for serum dupilumab concentration.
- Perform serum sampling for ADA.

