2.1.4.3 Laboratory safety variables

Clinical laboratory data consists of blood analysis, including hematology, clinical chemistry, and urinalysis. Clinical laboratory values after conversion will be analyzed into standard international units and international units will be used in all listings and tables.

Blood samples for clinical laboratories will be taken at Visit 1(Week -4±1), Visit 2 (Week 0), Visit 7 (Week 16), Visit 8 (Week 24), Visit 9 (Week 40), Visit 10(Week 52), Visit 11(Week 64) and early termination unless otherwise specified. The laboratory parameters will be classified as follows:

- Hematology
 - **Red blood cells and platelets and coagulation:** hemoglobin, hematocrit, red blood cell count, platelet count
 - **White blood cells:** white blood cell count, neutrophils, lymphocytes, monocytes, basophils, eosinophils
- Clinical chemistry
 - **Metabolism:** glucose, total cholesterol, total protein, creatine phosphokinase
 - **Electrolytes:** sodium, potassium, chloride, bicarbonate
 - **Renal function:** creatinine, blood urea nitrogen, uric acid
 - **Liver function:** alanine aminotransferase, aspartate aminotransferase, alkaline phosphatase, lactate dehydrogenase, total bilirubin (in case of values above the normal range, differentiation in conjugated and non-conjugated bilirubin), albumin
 - **Pregnancy test:** Serum β -human chorionic gonadotropin (all female patients) will be performed at screening (V1) in women of childbearing potential, and a urine dipstick pregnancy test will be performed at V2 prior to randomization and every 4 weeks

thereafter. A negative result must be obtained at V1 and V2 prior to randomization. In case of positive urinary test the study treatment will be withheld and a serum pregnancy test to confirm the pregnancy should be performed as soon as possible. Pregnancy will lead to definitive treatment discontinuation in all cases.

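### SAP Table 3 leaves the Week 52 laboratory window open-ended and gives Week 64 none, so Week 64 laboratory values drop out of the by-visit summaries or, probably rarely, are shown as Week 52

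*SAP*

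**What the plan says.** **Schedule.** SAP Section 2.1.4.3 lists the laboratory visits, ending with "Visit 9 (Week 40), Visit 10(Week 52), Visit 11(Week 64) and early termination unless otherwise specified". Protocol Section 10.1.15 (Visit 11, Week 64) agrees: "Obtain blood samples" heads an item covering hematology and serum chemistry. The flow chart in Protocol Section 1.2 also marks clinical laboratory testing at Week 64.

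**Windows.** SAP Section 2.5.4 says of the safety variables: "All available values from central lab will be assigned to the appropriate visit window". In the Week 52 row of Table 3, "Visit 10 (Week 52) 365 323-406 >322", the entries after target Day 365 are vital signs (323-406) and then clinical laboratory tests (>322). The Week 64 row begins "Visit 11 (Week 64) 449 >406", where >406 is the vital signs window; the laboratory cell is empty.

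**Selection rule.** If one window holds several values of the same test, "the one closest to the targeted visit date will be used for the by-visit summary"; a tie goes to the latest.

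**Use.** SAP Section 2.4.5.3 plans laboratory summary statistics at every time point after baseline, and plots of mean change over time.

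**The concern.** The plan collects laboratory data 12 weeks after the end of treatment but gives them no place in the by-visit output. Because the Week 52 window never closes, every Week 64 value is assigned to it. It then either loses to a sample nearer Day 365 or stands in for a missing Week 52 value.

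In the first case the group mean and mean change at Week 64 are not tabulated or plotted. A shift after stopping drug, for example in eosinophils, would then not appear as a group trend. In the second case a value from a patient more than 13 weeks past the last dose is labelled Week 52.

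Nothing in Section 2.5.4 limits the by-visit laboratory summary to the treatment epoch. The same section does impose that limit on the on-treatment efficacy sensitivity analyses.

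**Working it through.** **Inputs.** Target days from Table 3: Week 16 = 113, Week 24 = 169, Week 40 = 281, Week 52 = 365, Week 64 = 449. Visit tolerance is ±3 days (Protocol Section 10.1). The last IMP dose is at Week 50 (SAP Section 1.4.1). The treatment epoch ends at last IMP + 14 days and the treatment-emergent period at last IMP + 98 days (SAP Section 2.1.4).

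**1. Reproduce the plan's windows.** Boundaries are midpoints between the target days of consecutive visits with planned laboratory tests:

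- Weeks 16 and 24: (113 + 169)/2 = 141
- Weeks 24 and 40: (169 + 281)/2 = 225
- Weeks 40 and 52: (281 + 365)/2 = 323
- Weeks 52 and 64: (365 + 449)/2 = 407

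These give 141-224 and 225-322 for laboratory tests at Weeks 24 and 40, and the lower limit >322 at Week 52, all as printed. They also give 323-406 and >406 for vital signs at Weeks 52 and 64, as printed. Only the missing upper limit for laboratory tests departs from the rule.

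**2. Locate the Week 64 sample.** 449 ± 3 is Days 446-452, all above 322, so every such sample is assigned to Week 52. Its distance from target is 446 − 365 = 81 to 452 − 365 = 87 days.

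**3. Apply the closest-to-target rule.** A sample from Days 323-406 is at most 42 days from Day 365 (365 − 323 = 42; 406 − 365 = 41). Since 42 < 81, it always displaces the Week 64 sample.

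| Sample days | Week 52, as written | Week 64, as written | Week 52, 323-406 | Week 64, >406 |
|---|---|---|---|---|
| 365 and 449 | 365 | none | 365 | 449 |
| 406 and 446 | 406 | none | 406 | 446 |
| 300 and 449 | 449 | none | missing | 449 |
| 449 only | 449 | none | missing | 449 |

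**4. Time off drug.** Week 50 is Day 1 + 50 × 7 = 351. The Week 64 sample falls 446 − 351 = 95 to 452 − 351 = 101 days after that dose. The treatment epoch ends on Day 351 + 14 = 365 and the treatment-emergent period on Day 351 + 98 = 449.

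**5. Compare other assessments.** Vital signs and urine pregnancy tests (Table 3), nasal endoscopy and the rhinosinusitis VAS with sense of taste (Table 4), and serum dupilumab and anti-drug antibodies (Table 5) are all scheduled at Week 64 in the flow chart, and all have a Week 64 window of >406. The open-ended hepatitis B viral load and ECG windows do no harm, because neither test is scheduled at Week 64.

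**The case against.** A cell lost in reading the PDF does not explain this: >322 has no upper limit and would overlap any Week 64 window. The serious objections concern reach, and most of them stand.

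- **On-treatment summaries.** A reader might infer that off-drug values contaminate these. They do not. SAP Section 2.4.5 takes the endpoint value at the end of treatment or, failing that, from before the end of the treatment epoch, and limits worst values to the treatment epoch or EOT.
- **Recovery after stopping.** A reader might infer that it cannot be seen at all. PCSA incidence covers the treatment-emergent period, to Day 449 for a Week 50 last dose; only samples on Days 450-452 fall outside it. SAP Section 2.4.5.3 has a separate normalization analysis for elevated liver tests, with a category for recovery after discontinuation, and Protocol Section 11.4.3.1.3 plans flagged listings. What is missing is the group summary.
- **Database lock.** Under SAP Section 4 the lock follows the last Week 52 visit, and later data go to a CSR addendum. Many Week 64 samples may therefore miss the main report whatever Table 3 says. The defect still affects samples available at lock, and the addendum has no windows of its own.
- **Numbers affected.** A reader might infer that every patient's Week 64 panel goes unreported, or assume that 5-10% of 120 patients per arm, 6 to 12, are mislabelled. Neither is supported. Some panels would be shown as Week 52, not every patient will have a Week 64 panel, and the documents give no rate of missing Week 52 samples. Mislabelling needs a Week 64 sample and no other laboratory value after Day 322, and Protocol Section 10.3.1 does not list laboratory tests among the return assessments after early discontinuation.
- **Inference.** The safety analysis is descriptive, so no hypothesis test is affected.

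**Conclusion.** The point holds as a minor but definite error in Table 3. That a Week 64 sample loses its visit row when a Days 323-406 sample exists follows from the text alone, and it conflicts with the SAP's own plan to summarise every time point after baseline. Reporting a Week 64 value as Week 52 also follows from the text, but only for patients with no other laboratory value after Day 322. The judgement that they are few rests on how narrow that condition is, not on a figure in the documents. The 95-101 day interval assumes a last dose at Week 50 and a Week 64 visit within tolerance. The effect is confined to the by-visit laboratory tables and mean-change plots, in the CSR and in the addendum.

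**What to change.** In SAP Table 3, set the clinical laboratory windows to 323-406 for Week 52 and >406 for Week 64, and state that they apply to both the CSR and the addendum. The cost is two table cells and one sentence. Data collection does not change, and the windows then match the vital signs column. At the main lock the Week 64 row will be partial, so its patient count should be shown. The same edit could correct the cross-reference in SAP Section 2.4.5, which points to Section 2.5.3 for the safety windows although they are in Section 2.5.4.

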### 10.1 VISIT SCHEDULE

This section describes how the visits are carried out, in chronological order (according to the flow chart [Section 1.2](#) and identical to the order shown in the e-CRF):

The clinical trial consists of three periods, using an add-on therapy approach to INCS:

- Run-in Period (28 days+/- 3 days; V1).
- Randomized treatment period (up to 52 weeks +/- 3 days; Visits 2-10).
- Post-treatment Period (12 weeks; +/- 3 days V11).

The study visits occur on the planned dates (relative to the first injection), as scheduled. The visit schedule should be adhered to within the  $\pm 3$  day visit window.

If a patient is prematurely discontinued from treatment, every attempt should be made for the patient to return to the study site as soon as possible after last IMP administration to perform all assessments planned at the EOT visit and patients will be asked and encouraged to return to the study site for the visit scheduled as described in [Section 10.3.1](#) (early discontinuation) for a 12-week follow up.

Prior to all screening assessments, after discussion of participation in the study, the written consent form [REDACTED] must be signed and dated (see [Section 12.2](#)). At selected sites, requirements for collection of samples for a nasal biomarkers substudy will be included in a separate written informed consent.

Although the screening assessments for this study are grouped under the heading of a single visit in this protocol, it is possible for them to be performed over more than 1 site visit if necessary, as long as the run-in period window prior to Day 1 (V2) is respected. These patients do not need to sign a new consent form and be allocated a new patient number within this same window.

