#### **10.1.14 Visit 10 (Week 52): End of treatment**

- PRO Patient administration in the e-diary:
  - Daily symptoms of NC, loss of smell and anterior and posterior rhinorrhea,
  - SNOT-22,
  - VAS for rhinosinusitis,
  - Reduced sense of taste symptom severity score,
  - QoL (EQ-5D),
  - ACQ-6 (for patients with asthma).

- Health care resource utilization via e-CRF.
- Inquire about AEs/SAEs and background therapy tolerability.
- Collect IMP and NIMP boxes
- Record all medication use with start date and dose in the e-CRF.
  - Check for use of prohibited medications,
  - Complete rescue medication/surgery page (s) of e-CRF. Use of oral steroids for rescue treatment of worsening nasal polyps or for another reason will be captured by the Investigator (or designee) on the appropriate page(s) of the e-CRF page and the date and dosing information (daily dose, duration, INN) will be informed. Details on planned date for surgery, type, and outcome (whenever possible) of surgery will be recorded in a specific e-CRF page. If surgery is performed during the study treatment period or follow-up an AE or SAE page will be completed.
- Call IVRS/IWRS to register visit and obtain NIMP (NASONEX) box(es) if needed.
- Download e-diary and review the data; remind patient to bring the device to the next visit.
- Perform blood sampling for serum dupilumab concentration.
- Perform spirometry (for patients with asthma) and record FEV1, FVC and FEF 25-75 result in the e-CRF.
- Measure vital signs (blood pressure, heart rate, respiration rate, body temperature, weight).
- Perform physical examination.
- Perform ECG (refer to [Section 9.4.6](#)).
- Perform CT scan (unless not approved by local ethics committee).
- Perform nasal endoscopy and send to Central Reader.
- Administer smell test (UPSIT).
- Obtain blood samples for (prior to IMP):
  - Hematology (see [Section 9.4.2](#) for details),
  - Serum chemistry (see [Section 9.4.2](#) for details).
- Perform blood sampling for Hepatitis B viral load (for patients in Japan [or other countries/regions if there is local regulatory requirement] who are HBsAg negative and HBsAb positive at V1).
- Perform serum sampling for ADA.
- Obtain serum and plasma for biomarkers, see [Section 9.5.2](#)
- Perform blood sampling for stored serum for those patients who have signed a specific informed consent form.
- Perform blood sampling for total IgE.

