### 10.3.1 Permanent treatment discontinuation with investigational medicinal product(s)

Permanent treatment discontinuation is any treatment discontinuation associated with the definitive decision from the Investigator or the patient not to re-expose the patient to the IMP at any time.

Patients who discontinue treatment permanently during the treatment period will be assessed as soon as possible using all procedures normally planned for the End-of-treatment Visit with the exception of CT Scan. Patients who discontinue early during the post-treatment period will be assessed as soon as possible using all procedures normally planned for the end-of-study (EOS) Visit.

For patients in whom the surgery date is scheduled after the planned end of study, a follow up contact(s) should be performed around the time of planned surgery to document the surgery date. Surgery data will be collected only until e-CRF Closure and EOS will not be delayed.

Patients will also be instructed to:

- Return to the study site for evaluations of NPS, SNOT-22, at:
  - Week 24, Week 52: If the ETD visit occurred between Week 0-Week 16,
  - Week 52: If the ETD visit occurred between >Week 16-Week 40,
  - Week 64 (EOS): If the ETD visit occurred between >Week 40-Week 52.
- Return and have a CT Scan performed as scheduled at Week 24 and 52.

Patients who discontinue prior to week 40 will have the following assessed through week 52, patients who discontinue after week 40 will have the following assessed through week 64:

- Perform PK and ADA sampling at the initially scheduled visits for these assessments
- Continue to complete the e-diary for nasal congestion, loss of smell daily symptom and anterior/posterior rhinorrhea evaluation
- Continue on MFNS stable dose but patients are not required to complete the INCS use daily in the e-diary after ETD.
- Advise patients with comorbid atopic conditions (such as asthma) not to adjust their treatment without consultation with their physicians.
- Report any AE up to the last scheduled visit (Week 52 or Week 64 depending on the discontinuation date).
- Contact the Investigator during the post treatment period up to the EOS visit if the symptoms worsen requiring medical attention.

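### The Week 24 blood-biomarker window in SAP Table 5 opens straight after the first dose, so an early-termination sample can be summarised as the Week 24 value

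*SAP*

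**What the plan says.** SAP 2.1.6 schedules the blood biomarkers at Week 0, Week 24 and Week 52. The Visit 8 row of Table 5 (SAP 2.5.4) reads "Visit 8 (Week 24) 169 1+-266 141-224 141-266": target Day 169, then the windows for blood biomarkers, drug concentration and ADA in that order. The table footnote defines the opening symbol as "1+: after 1st dose date/time or randomization date if patient is not treated". The assignment rule is "All available values of measurements will be assigned to the appropriate visit window". Where several values share a window, "the one closest to the targeted visit date will be used for the by-visit summary".

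Protocol 10.3.1 has patients who permanently stop treatment "assessed as soon as possible using all procedures normally planned for the End-of-treatment Visit with the exception of CT Scan". The end-of-treatment visit (Protocol 10.1.14) lists "Obtain serum and plasma for biomarkers, see" Section 9.5.2, and total IgE separately. After early termination, 10.3.1 keeps NPS, SNOT-22, CT, PK, ADA and diary follow-up. It names no further blood-biomarker sample.

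**The concern.** A value labelled Week 24 should come from about Week 24. Here the lower bound is the first dose, all available values count, and the early-termination visit produces a sample that nothing later replaces. The closest-to-target rule helps only a patient who also has a sample nearer Day 169, and someone who stops before Visit 8 normally has none.

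SAP 2.4.6.2 plots biomarker values, changes and percent changes by visit and treatment group. The Week 24 points would mix on-schedule samples with samples taken after much shorter exposure. If dropout differs between arms, so does the mix. Week 24 biomarker and drug-concentration summaries would also describe different times for the same patients.

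**Working it through.** The plan states no figure to reproduce. The check applies the window rule and then sizes the effect under stated assumptions.

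**1. Assignment.** Keep values from Day 2 to Day 266 and take the one closest to Day 169.

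| Biomarker sample day(s) | Value used for Week 24 | Distance from target |
|---|---|---|
| 15 | Day 15 | 154 days |
| 43 | Day 43 | 126 days |
| 120 | Day 120 | 49 days |
| 168 and 200 | Day 168 | 1 day |
| 169 and 250 | Day 169 | 0 days |
| 280 | none (goes to Week 52) | – |

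The window reaches 169 − 2 = 167 days before the target and 266 − 169 = 97 days after it.

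**2. Same visit, other analytes.** For an early-termination visit on Day 90, Table 5 puts drug concentration in Week 16 (71-140), ADA in Week 16 (85-140) and biomarkers in Week 24. For Day 36, it puts drug concentration in Week 4 (22-70), ADA in Week 8 (1+ to 84) and biomarkers in Week 24.

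**3. Where the bounds come from.** The upper bound fits the midpoint of the Week 24 and Week 52 targets: (169 + 365)/2 = 267. The lower bound fits no midpoint. The midpoint of the biomarkers' own first two visits is (1 + 169)/2 = 85. The midpoint of Week 16 and Week 24, which the Day 141 bounds follow, is (113 + 169)/2 = 141. Days 2 to 140 make up 139 of the window's 265 days (52%).

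**4. Share of patients.** The 25% dropout comes from the sample-size section (Protocol 11.1, SAP 1.3). My assumptions are that dropout is uniform over Days 1-168 and that every dropout gives an early-termination sample.

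- Share before Day 141 = dropout × 140/168.
- At 25%: 0.25 × 0.833 = 0.208.
- At an illustrative 10%: 0.10 × 0.833 = 0.083.
- Mean sampling day, averaging over Days 2-140: Day 71.

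**5. Effect on the Week 24 decline.** The documents give no marker kinetics. I assume an exponential decline with half-life h weeks. The fraction of the Week 24 decline reached at t weeks is (1 − 2^(−t/h)) / (1 − 2^(−24/h)), averaged over Days 2-140 with t = day/7. Understatement = share × (1 − fraction).

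| h (weeks) | Fraction reached | Understated, 25% dropout | Understated, 10% dropout |
|---|---|---|---|
| 4 | 0.74 | 0.208 × 0.26 = 5% | 0.083 × 0.26 = 2% |
| 8 | 0.61 | 0.208 × 0.39 = 8% | 0.083 × 0.39 = 3% |
| 16 | 0.52 | 0.208 × 0.48 = 10% | 0.083 × 0.48 = 4% |

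**The case against.** The strongest reply is that opening the first post-baseline window right after the first dose is this SAP's general convention. Vital signs, laboratory tests, EQ-5D and ADA all do so. Drug concentration and ADA start Week 24 at Day 141 because they have a Week 16 visit, which the blood biomarkers lack. That stands: the contrast within Table 5 does not show an internal contradiction. But the convention does little harm when the first target is Week 4, 8 or 16. With a first target of Day 169 it lets a two-week sample stand for Week 24.

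The size is also fairly disputed. The 25% is a planning allowance, not a rate of patients who stop drug and still attend for sampling, so 21% is an upper bound on these inputs. The half-lives are assumptions.

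A reader might infer three stronger points that the documents do not support.

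- **CT and the co-primary.** The Visit 8 row of Table 4, "Visit 8 (Week 24) 169 141-224 1+-266 141-266", gives CT the same wide window, which suggests that an early scan could become the Week 24 Lund-Mackay value (co-primary in Japan, key secondary elsewhere). Protocol 10.3.1 excludes CT at early termination and keeps it at Weeks 24 and 52. Protocol 10.1 does ask patients to return "as soon as possible after last IMP administration to perform all assessments planned at the EOT visit" without repeating the exception, but it refers on to 10.3.1, as does 10.3.4. For the primary analyses, Table 4 takes scheduled measurements only. What remains is wording: 10.3.5, on study withdrawal, asks for end-of-treatment procedures and does not repeat the exception.
- **Arm B after the switch to q4w.** Day 266 could admit a sample taken after Week 24 in Arm B, but only when no nearer one exists. The bound follows the Week 24/52 midpoint, and ADA and UPSIT use it too. I do not count it as a defect.
- **A Week 2 threshold.** The SAP has none. The window opens after the first dose, and samples after Day 266 go to Week 52.

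**Conclusion.** The point holds for the blood biomarkers in Table 5, at low severity. For a patient who stops before Visit 8 and has no sample nearer Day 169, the rule as written reports an early-termination sample as Week 24. At most about 21% of patients would be affected at 25% dropout, or about 8% at 10%, if dropout is uniform and every dropout is sampled. The group decline at Week 24 would then be understated by roughly 2% to 10%, under assumed half-lives of 4 to 16 weeks.

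Biomarkers are an exploratory objective (SAP 1.2.3), Table 5 serves descriptive by-visit summaries, and the visible text of SAP 2.4.6.2 plans only summaries and plots for them. No confirmatory test, key endpoint or alpha allocation is affected.

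**What to change.** In Table 5, change the Week 24 blood-biomarker window to Days 141-266, as for ADA, and report early-termination samples taken before Day 141 on a separate row. Day 85, the midpoint of the biomarkers' own visits, is a defensible but weaker bound: it would still label a Day 90 sample as Week 24. The change is one cell and one row. Fewer patients will have a Week 24 value, but no data are lost.

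Separately, reconcile Protocol 10.3.5 with the CT exception in 10.3.1, and state in the SAP whether a scan taken at study withdrawal counts as scheduled. If the CT window in Table 4 is tightened as a safeguard, use 141-266. CT has no Week 40 window and its Week 52 window starts after Day 266, so an upper limit of 224 would leave Days 225-266 unassigned.
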